4. PROTOCOL DEVIATION MANAGEMENT AND REPORTING

Any deviation from the protocol should be documented on the "Protocol Deviation" case report form.

5. ADVERSE EVENT MANAGEMENT AND REPORTING

Any adverse event should be documented on the Adverse Event case report form. A record of all adverse events, including details of the nature, onset, duration, severity, relationship to the device, relationship to the operative procedure and outcome, will be made on the relevant section(s) of the subject's CRF. The subject will be questioned about any adverse event(s) at each subsequent follow-up assessment visit.

Any serious adverse events (SAE/SADE/USADE) must be reported to head of institution and must be notified to other institutions participating in this study in accordance with Ethical Committee and Ethical Guidance for clinical study including human subject.

Adverse Event (AE):

An adverse event is any untoward medical occurrence in a patient receiving an investigational medical device that does not necessarily have to have a causal relationship with the device under investigation. An AE can therefore be any unfavorable and unintended sign (including abnormal laboratory finding), symptom, or condition temporally associated with the use of a medical device whether or not considered related to the medical device.

Serious Adverse Event (SAE):

A serious adverse event is an adverse event that

- a) led to death
 - b) led to a serious deterioration in the health of the patient that
 - c) led to fetal distress, fetal death or a congenital abnormality or birth defect
- 1) resulted in a life-threatening illness or injury

- 2) resulted in a permanent impairment of a body structure or a body function
- 3) resulted in medical or surgical intervention to prevent permanent impairment to body structure or body function
- 4) required in-patient hospitalization or prolongation of existing hospitalization

A planned hospitalization for a pre-existing condition, or a procedure required by this protocol, without serious deterioration in health, is not considered a serious adverse event.

Adverse Device Effect (ADE):

An ADE is any untoward and unintended response to an investigational medical device.

Serious Adverse Device Effect (SADE):

A SADE is any untoward and unintended response investigational medical device that has resulted in any of the consequences characteristic of a serious adverse event or that might have led to any of these consequences if suitable action had not been taken or intervention had not been made or if circumstances had been less opportune.

Unanticipated serious adverse device effect (USADE)

Serious adverse device effect which by its nature, incidence, severity or outcome has not been identified in the current version of the risk analysis report (see section 10) .

6. MPLANT RETRIEVAL AND ANALYSIS OF REMOVED IMPLANTS

Should any implant failures occur, please contact the Study Manager or any other Zimmer Biomet personnel to coordinate the implant retrieval process.

7. STATISTICAL ANALYSIS PLAN

7.1 SAMPLE SIZE CALICULATION

The primary analysis for the study will compare the maintenance rate of immediate post-operative reduction position on the 3 week post-operative x-ray for Investigational (with ASS technique) vs. Control (without ASS technique). Sample size calculations for this study are done using data found in a paper by Maehara et al⁵. In this study, 87.5% of the patients with ASS technique were maintaining immediate post-operative reduction position, as compared to 72.7% in the conventional cohort. Our sample size calculation assumes the result in this study will be similar to what is reported in Maehara et al.

The null hypothesis is that the maintenance rate of immediate post-operative reduction position for the investigational group (with ASS technique) is less than or equal to that of the patients operated without ASS technique. The alternative hypothesis is the maintenance rate of immediate post-operative reduction position for the investigational group (with ASS technique) is greater than that of the patients operated without ASS technique.

Null Hypothesis : $H_0: \pi_A - \pi_B \leq 0$

Alternative Hypothesis : $H_A: \pi_A - \pi_B > 0$

Where π_A represents the maintenance rate of immediate post-operative reduction position in investigational group on the 3 weeks postoperative CT and π_B represents the maintenance rate of immediate post-operative reduction position in control group on the 3 weeks postoperative CT.

If we reject the null hypothesis, we can conclude that the ZMM CM Asia with ASS technique is superior to the conventional technique in trochanteric fracture with regard to the maintenance rate of immediate post-operative reduction position.

The sample size calculation was conducted anticipating the use of a Pearson's Chi-square test.

Alpha level: 5% (two sided)

Power: 80%

Investigational group maintenance rate for reduction position: 87.5%

Control group maintenance rate for reduction position: 72.7%

The resulting calculation gives $n=113$ per group. 120 patients per group will allow for up to 5% attrition.

Overall population per protocol: 240

7.2 DETAILED DESCRIPTION OF RANDOMIZATION

In this study, patients will be randomized in one of the two treatment arms: ZMM CM Asia with ASS technique (Investigational group) or ZMM CM Asia without ASS technique (Control group). The randomization scheme is based on equal numbers per group. The randomization will occur via a random number generator (computer) using a blocked randomization procedure. The block size will not be disclosed to the sites, and the doctor or other health care professional will not have influence on the randomization scheme. Sealed opaque envelopes, which will be prepared based on predetermined randomization assignment, will be provided to each study site before study initiation.

7.3 HANDLING OF MISSING AND INCOMPLETE DATA

Data will be considered “missing” for the primary endpoint if this outcome cannot be determined or is unavailable for a subject. Every effort will be made to collect the data necessary to evaluate the primary endpoint. Subjects who have been lost to follow-up and/or are missing CT data at 3 weeks will not be included in the primary study analysis.

Sensitivity analyses will be performed to assess the impact of missing data on the primary study analysis. These analyses may include a best-case and worst-case imputation as well as a tipping point analysis.

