3.3 SUBJECT WITHDRAWAL

It is recognized that the subject's participation in this trial is entirely voluntary, and that she/he may refuse to participate and may withdraw from participation at any time without jeopardy to any future medical care. It is also recognized that the investigator, at his/her discretion, may withdraw a subject from this study based upon his/her professional judgment. In event of subject withdrawal, applicable local procedures should be followed.

If a patient is withdrawn or rescinds their consent, a "Lost to Follow-up" case report form should be completed detailing the reason for the patient withdrawal. The site should also notify their Ethical Committee (EC) if applicable. If a patient is withdrawn from the study by the investigator, the patient should be notified of their removal by a letter from the site or according to the local EC.

It is required that patients return within the defined follow-up period to complete all study assessment forms and radiographs. Patients that miss or will not return for follow-up are not considered "protocol deviations" or "lost to follow-up."

Specific criteria for withdrawal (if applicable)

If patients meet any of the following criteria, a subject withdrawal form should be completed, and below data documented on the form:

1. Patient rescinds consent in writing: Date of occurrence
2. Patient Death: Reason and date of death should be documented
3. Implant Removal: Date of revision, all component part numbers removed, and reason for revision

Replacement of individual subjects after withdrawal

Subjects will not be replaced, unless they do not have surgery or intraoperatively it has been recognized the patient is not eligible for a treatment with ZNN CM Asia.

Follow-up of subjects withdrawn from treatment

Subject withdrawn from the study will obtain standard medical treatment as foreseen at the investigational site.

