7.4 DATA ANALYSES

Data will be analysed using SAS 9.0 or higher. The Type I error rate for the primary study analysis will be 0.05. Comparisons for secondary, exploratory, and safety analyses will be two-sided comparisons using $\alpha = 0.05$, with no adjustment for multiple comparisons.

Primary Analysis: The primary analysis will be performed on the set of patients with non-missing CT data at 3 weeks (Full Analysis Set (FAS)). Sensitivity analyses will be presented for the intention-to-treat (ITT) patient group. A two-tailed Pearson’s Chi-Square test at $\alpha = 0.05$ will be used to assess the study hypotheses and determine whether there is a statistically significant difference between investigational and control groups with regard to the maintenance rate of immediate post-operative reduction position.

Secondary Analysis: Analyses for secondary endpoints will be on the FAS, and will only use those cases with complete data for the endpoint being analysed.

Continuous data (e.g. age, BMI) will be reported using mean, standard deviation, median, and range. Comparisons between Investigational vs Control groups with regard to continuous baseline and secondary outcomes will be performed using standard statistical tests and will be chosen as appropriate for the scale and distribution of the measures being analyzed. For example, a t-test, Wilcoxon test, or one-way ANOVA (as appropriate) may be performed to assess differences in means/medians.

Categorical data (e.g. gender, classification of fracture) will be reported using frequency and percentage. Comparisons of Investigational vs Control with regard to categorical baseline, secondary and safety outcomes will be performed using standard statistical tests and will be chosen as appropriate for the scale and distribution of the measures being analyzed. For example, categorical outcomes may be compared for investigational and control groups using the Pearson’s chi-square test.

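### Sections 7.3 and 7.4 make no exception for a documented loss of reduction re-operated before the 3-week CT, so a known failure without that CT leaves the primary analysis

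*Combined protocol and SAP*

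**What the plan says.** The primary endpoint (Section 2.3) is whether the reduction position seen immediately after surgery still holds at 3 weeks. Section 2.5 has a central reviewer compare the two CTs with patient identifiers removed.

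Section 7.3 treats the endpoint as missing "if this outcome cannot be determined or is unavailable for a subject", promises that "Every effort will be made to collect the data necessary to evaluate the primary endpoint", and then sets the exclusion: "Subjects who have been lost to follow-up and/or are missing CT data at 3 weeks will not be included in the primary study analysis". Section 7.4 says: "The primary analysis will be performed on the set of patients with non-missing CT data at 3 weeks (Full Analysis Set (FAS".

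Two kinds of sensitivity analysis are committed. Section 7.4 says: "Sensitivity analyses will be presented for the intention-to-treat (ITT) patient group". Section 7.3 commits to sensitivity analyses for missing data but leaves the methods open: "These analyses may include a best-case and worst-case imputation as well as a tipping point analysis".

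Section 3.3 lists implant removal among the withdrawal criteria, to be recorded on a subject withdrawal form with these details: "Implant Removal: Date of revision, all component part numbers removed, and reason for revision". A separate, general sentence in the same section reads: "If a patient is withdrawn or rescinds their consent, a 'Lost to Follow-up' case report form should be completed". Withdrawn patients then receive the site's standard care. Section 10 lists loss of reduction or fixation among the foreseeable adverse events.

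**The concern.** Take a patient whose reduction is lost in the second week, whose implant is removed for that reason, and who has no CT at 3 weeks. The endpoint question has an answer: the reduction was not maintained. Yet membership of the primary set turns on the 3-week CT and on follow-up status, so the patient leaves both numerator and denominator.

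The exclusion is then caused by the outcome itself. It raises the observed maintenance rate in whichever arm loses the patient. A control failure dropped narrows the difference; an ASS failure dropped widens it. The trial rests on one chi-square test at 0.05, so a handful of such patients could matter if the result is close.

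A related gap is that nothing bars a CT taken after revision from being read as the 3-week CT. It would show the revised construct, not whether the first reduction held.

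**Working it through.** **Inputs.** From Section 7.1: maintenance 87.5% (ASS) and 72.7% (control), two-sided alpha 0.05, power 80%, Pearson chi-square, 113 per group, 120 enrolled. *Assumptions:* the share or number of failures re-operated without a 3-week CT, since the documents give none; that the planning rates count such patients as failures; and, for illustration, that all other patients are evaluable (120 per arm).

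**1. The plan's own figure.** With pooled rate p̄ = (0.875 + 0.727)/2 = 0.801,

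n = [1.960·√(2·0.801·0.199) + 0.842·√(0.875·0.125 + 0.727·0.273)]² / 0.148² = 113.05.

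Rounded up this is 114; the stated 113 has power 79.98%, so it reproduces. At 120 per arm power is 82.3%.

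**2. Same share f of failures dropped in both arms.** Observed rate = (1 − q)/(1 − f·q), with q = 0.125 (ASS) and 0.273 (control). Expected failures are 120 × 0.125 = 15 and 120 × 0.273 = 32.8.

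| f | Dropped, ASS / control | Observed rates | Difference | Power |
|---|---|---|---|---|
| 0 | 0 / 0 | 87.5% vs 72.7% | 14.8 points | 82.3% |
| 5% | 0.75 / 1.6 | 88.1% vs 73.7% | 14.3 points | 80.7% |
| 10% | 1.5 / 3.3 | 88.6% vs 74.7% | 13.9 points | 78.9% |

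The bias is towards no difference, because the control arm has more failures to lose.

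**3. Failures dropped in one arm only.** Observed rate = 120p/(120 − k).

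| k | Control only: difference, power | ASS only: difference, power |
|---|---|---|
| 1 | 14.2 points, 79.3% | 15.5 points, 86.2% |
| 2 | 13.6 points, 75.9% | 16.3 points, 89.6% |
| 3 | 12.9 points, 72.2% | 17.0 points, 92.4% |

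The higher power in the last column comes from bias, not information.

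**4. Type I error.** With 72.7% in both arms, each failure dropped with probability f, and full enumeration of the two-sided test: 5.0% with none dropped; 5.0% with f = 5% or 10% in both arms; 5.4% or 6.5% with f = 5% or 10% in one arm only.

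**5. Can it change a verdict?** Pearson chi-square without continuity correction.

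- Near the planned rates: 105/120 vs 87/120 gives p=0.004. Dropping 1, 2 or 3 control failures gives p=0.005, 0.007 or 0.010. Eight dropped (87/112) gives p=0.048; nine (87/111) gives p=0.064.
- Near the boundary, ASS failure dropped: 99/120 vs 87/120 has pooled rate 186/240 = 0.775, so χ² = 0.100²/[0.775·0.225·(2/120)] = 3.44, p=0.064. Drop one ASS failure: 99/119 vs 87/120 gives χ² = 3.96, p=0.047.
- Near the boundary, control failure dropped: 100/120 vs 87/120 gives p=0.043; 100/120 vs 87/119 gives p=0.055.

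**The case against.** Five points can fairly be made for the plan.

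- **Missing is defined by determinability.** An analyst could say that a documented loss of reduction is determined and so not missing. That reading leaves real ambiguity, but the exclusion sentence in 7.3 and the set definition in 7.4 do not depend on it; both look to the 3-week CT.
- **The event is narrow.** The patient must lose reduction, be re-operated within about 3 weeks and have no CT in the window. Section 1.1 cites 14% re-displacement at two weeks without mentioning re-operation. This stands: every count above is an assumption.
- **The larger effects need lopsided loss.** Three ASS failures and no control failures dropped means losing 3/15 = 20% of the expected failures in one arm and none of about 33 in the other. Nothing in the documents supports that. This stands too.
- **The planning rates come from a cited paper that is not available here.** If they also rest on imaged patients only, the power figures above do not measure a loss against plan. This stands as a limit on steps 2 and 3.
- **Sensitivity analyses are committed.** They are, but they do not alter the primary result, the named methods are optional, and the ITT analysis has no scoring rule for this patient.

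A reader might infer more in three places. First, that the plan expressly removes re-operated patients: it never mentions them, and the exclusion follows from general wording. Second, that the rule favours ASS or breaks type I error control: with equal shares dropped it does neither. Third, that Section 9, which lists implant removal and component revision as lost to follow-up, shuts out even a revised patient who has a CT: 7.3 does not cite that list, which serves follow-up percentages. Nor does Section 3.3 tie implant removal directly to the Lost to Follow-up form; the general withdrawal sentence reaches it only by inference.

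**Conclusion.** The point holds as a gap in the primary analysis rule. Followed as written, Sections 7.3 and 7.4 drop a known failure when re-operation comes before the 3-week CT and no such CT exists. The likely size is small. With an equal 5% or 10% share of failures lost in both arms, the difference falls by 0.5 or 0.9 points, power stays at 80.7% or 78.9%, and type I error is unaffected. A result at the planned rates would survive the loss of eight control failures. The exposure is a result close to 0.05, where one patient can move it either way. The frequency of the event and its balance between arms are assumptions. The change is worth making before analysis because it is cheap and settles how a known outcome is scored.

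**What to change.** In Sections 7.3 and 7.4:

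- Keep in the primary analysis, scored as reduction not maintained, any patient with implant removal or component revision before the 3-week CT whose last image before re-operation shows loss of the immediate post-operative position. The existing central reviewer should read that image de-identified.
- Do not use a CT taken after revision to score maintenance.
- Where no pre-revision image exists, treat the outcome as missing in the primary analysis. In a committed sensitivity analysis, score a recorded reason of loss of reduction as a failure. This keeps a reason written by staff who know the arm out of the primary endpoint.
- Apply the same rule in the ITT sensitivity analysis, and commit to the worst-case and tipping-point analyses for outcomes that remain undetermined.

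As a minor wording point, reconcile the use of lost to follow-up in Sections 3.3 and 9 with 7.3. Section 3.3 also says that patients who miss follow-up do not count as lost.

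The cost is protocol and SAP wording and retrieval of the last image before re-operation. No patients or visits are added, and the required sample size does not change. Observed maintenance rates may be slightly lower.

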9. DATA REPORTING

Within 6 months of the study close the sponsor will present a final study report to summarize all data collected throughout the study duration, complications throughout the course of the data collection, and general findings.

The report will contain the results of all primary and secondary endpoints. Also, patient follow-up will be analyzed throughout the data collection according to the following definition and equations:

- Lost To Follow-Up:
1. Death
 2. Implant Removal: Date of revision, all component part numbers removed, reason for revision, and any relation to study device.
 3. Revision of Components: date of revision, all component part numbers removed, and reason for revision Consent Rescinded

**Bearing revisions in which only the polyethylene is replaced will not be withdrawn from the study.*

Percentage Follow-up = # Patients with Follow-Up x 100
(Theoretically due – Lost To Follow-Up)

Percentage Accounted for = (# with Follow-Up + Lost To Follow-Up) x 100
Theoretically due

Both the sponsor and investigators will make reasonable efforts to publish the results of this trial.

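### Sections 7.3 and 7.4 define different primary analysis sets: read literally, 7.3 can drop a patient whose 3-week CT is in hand because of a later event

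*Combined protocol and SAP*

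**What the plan says.** Four places in the combined protocol and SAP bear on who enters the primary analysis.

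- **Section 7.3** sets the exclusion: "Subjects who have been lost to follow-up and/or are missing CT data at 3 weeks will not be included in the primary study analysis". The same section counts primary-endpoint data as missing only when the outcome is unavailable or cannot be established.
- **Section 7.4** names the primary set: "The primary analysis will be performed on the set of patients with non-missing CT data at 3 weeks (Full Analysis Set (FAS")). It has no condition on follow-up status. Section 7.5 says the analysis will follow the methods of 7.4 and places it after a 6-month time point.
- **Section 9** lists what counts as lost to follow-up: death, implant removal, and a third item in which two reasons run together, "Revision of Components: date of revision, all component part numbers removed, and reason for revision Consent Rescinded". No time limit is given. The list is introduced as the definition for two follow-up percentages in the final report.
- **Section 3.3** uses the term in another way. A lost-to-follow-up form is completed when a patient is withdrawn or rescinds consent, whereas "Patients that miss or will not return for follow-up are not considered" protocol deviations or lost to follow-up. Death and implant removal appear there under a separate withdrawal form.

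**The concern.** The primary endpoint is complete once the immediate post-operative and 3-week images have been compared. What happens to the patient afterwards should not decide whether that result counts. Under the wording of 7.3 it can.

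Consider a patient whose 3-week CT shows re-displacement and whose nail is revised at week 8, or one with maintained reduction who dies at week 10. Both belong to the 7.4 set. Under 7.3, read with the section 9 list, both are excluded.

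Two things are at stake. First, removal or revision is plausibly more frequent in hips that have lost reduction, so the deletion could depend on the outcome being analysed. Investigators may also withdraw a subject at their discretion (3.3), and that triggers the lost-to-follow-up form. Second, two primary sets can be defended from the text, and nothing says which prevails. That choice should not remain open once results are known.

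**Working it through.** **1. The two rules side by side**

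| Patient | 7.3, read with the section 9 list | 7.4 |
|---|---|---|
| 3-week CT read, no later event | in | in |
| 3-week CT read, later death, removal, revision or rescinded consent | out | in |
| 3-week CT read, later visit simply missed | in (not lost to follow-up under 3.3) | in |
| No 3-week CT | out | out |

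The rules differ only in the second row.

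**2. The plan's own sample size (7.1)**

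Inputs: 87.5% with ASS, 72.7% without, two-sided 5%, 80% power, Pearson chi-square, 1:1 allocation. The mean rate is (0.875 + 0.727)/2 = 0.801.

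n = [1.960 × √(2 × 0.801 × 0.199) + 0.8416 × √(0.875 × 0.125 + 0.727 × 0.273)]² / 0.148²
= (1.960 × 0.5646 + 0.8416 × 0.5548)² / 0.021904 = 113.05 per group.

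This reproduces the stated 113 (114 if rounded up; power at 113 is 79.98%). With 5% attrition, 120 × 0.95 = 114 per group, and power is 80.3%.

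**3. Illustration A: a share f of re-displaced hips is dropped in each arm**

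The documents give no rate of revision, removal, death or withdrawal after week 3, so f is an assumption. Start from 114 per arm, with 114 × 0.125 = 14.25 expected failures with ASS and 114 × 0.273 = 31.12 without.

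Rate with ASS = 0.875 / (0.875 + 0.125(1 − f)); control rate = 0.727 / (0.727 + 0.273(1 − f)).

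Power = Φ[(difference − 1.960 × SE₀) / SE₁], where SE₀ is the pooled and SE₁ the unpooled standard error at the reduced group sizes.

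| f | Dropped, ASS / control | Rates, ASS / control | Difference (points) | Power |
|---|---|---|---|---|
| 0 | 0 / 0 | 87.5% / 72.7% | 14.8 | 80.3% |
| 0.10 | 1.4 / 3.1 | 88.6% / 74.7% | 13.9 | 76.8% |
| 0.20 | 2.9 / 6.2 | 89.7% / 76.9% | 12.8 | 72.6% |
| 0.30 | 4.3 / 9.3 | 90.9% / 79.2% | 11.7 | 67.7% |

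**4. Illustration B: deletion unrelated to outcome**

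If 2%, 5% or 10% (assumed) of evaluable patients were dropped at random, about 112, 108 or 103 per arm remain. Power is 79.5%, 78.3% or 76.0%, and the expected difference is unchanged.

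**5. Illustration C: the same number of failures dropped from each arm**

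Suppose 5% of each arm (114 × 0.05 = 5.7 patients) is dropped and all are failures. The rates become 0.875/0.95 = 92.1% and 0.727/0.95 = 76.5%. The difference rises to 0.148/0.95 = 15.6 points, and power to 88.9%. The direction of any distortion therefore depends on how deletions fall across the arms, which the documents do not tell us.

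**The case against.** The strongest reply is that 7.4 governs. It names and defines the primary set, 7.5 points to it, and the definition of missing in 7.3 does not fit a hip whose 3-week CT has been read. Section 7.3 does not refer to section 9, whose list serves report percentages and carries a footnote on polyethylene bearings that does not fit this nail system. The words on 3 weeks in 7.3 can also be read as limiting both conditions. On this view the follow-up phrase is merely redundant.

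Much of this stands. A reader might infer that the plan firmly deletes evaluable patients for later events. The documents do not support that, because it needs a list imported into 7.3 that 7.3 does not cite, against the more specific text of 7.4. Nor is it certain that later events would be fully known: the last required assessment is at 3 weeks, the 16-week visit is optional, and the schedule shows no 6-month visit.

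What does not stand is that nothing needs changing. Taking the phrase to mean ordinary no-shows is blocked by 3.3, and a programmer following 7.3 would have only the section 9 list or the withdrawal forms to work from. The sensitivity analyses in 7.3 address missing outcomes, whereas these are observed. The planned ITT sensitivity analysis could bring such patients back, but it does not settle the primary set. It is also unsafe to say that any distortion must work against ASS: illustration A shrinks the difference, but illustration C enlarges it.

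**Conclusion.** The inconsistency is real. Sections 7.3 and 7.4 give different primary analysis sets for patients with an evaluable 3-week CT and a later event, and the key term is used inconsistently in 3.3 and 9. The weight of the text favours keeping these patients, but the plan should not need a charitable reading to identify its primary population.

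The size cannot be established from the documents. If an assumed 10% to 30% of re-displaced hips were dropped in each arm, the expected difference would fall from 14.8 points to between 13.9 and 11.7, and power from about 80% to between 77% and 68%. These figures rest on the planning rates, on 114 evaluable patients per arm, and on an assumed fraction with no anchor in the plan. They show sensitivity and are not a forecast.

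The sample size of 113, raised to 120 per group, is unaffected. Patients with no 3-week CT are excluded under both rules and are outside this point. The wording should be fixed, but the design is not in question.

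**What to change.** Replace the exclusion sentence in 7.3 with wording such as:

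> Subjects whose primary endpoint (reduction status at 3 weeks relative to immediate post-operative) cannot be determined will not be included in the primary analysis. A subject with an evaluable primary endpoint remains in the FAS regardless of later death, implant removal, revision or withdrawal, unless consent to use data already collected is withdrawn.

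Use the same definition for the FAS in 7.4. That section now mentions only the 3-week CT, although the endpoint also needs the immediate post-operative position. State in section 9 that its list serves only the follow-up percentages.

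The cost is a few sentences of wording. No new patients, images or data are needed, and the sample size does not change. The amendment should be made and dated before results by arm are known.
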